We are currently piloting two patient-reported outcomes (PRO) measures for Type 1 and 2 SLE: The Fibromyalgia Severity Score (FSS) allows patients to indicate areas of pain, extent of fatigue, waking unrefreshed, and cognitive symptoms. The FSS was designed to diagnose fibromyalgia, but we have found this scale clinically useful to efficiently measure the current extent of Type 2 SLE symptoms. The Systemic Lupus Activity Questionnaire (SLAQ) is a 24-symptom patient-reported measure of SLE activity. It partially correlates with the physician-reported Systemic Lupus Activity Measure. We have found the SLAQ clinically useful in highlighting important symptoms for patients, but the current scoring system combines Type 1 and 2 SLE activity, resulting in an assessment that is not clinically actionable.

The proposed research will build a brief preliminary PRO measure that combines features of the FSS and the SLAQ to indicate the current degree of Type 1 and Type 2 SLE activity, allowing for rapid assessment and appropriate treatment in practice.

The overall objective of this study is to develop a composite measure based on our conceptual model of Type 1 and 2 SLE to distinguish between these two symptom complexes, and then conduct a pilot implementation study of the measure within Duke Rheumatology. The central hypothesis is that Type 1 and 2 SLE are clinically distinct components of SLE that, once distinguished, will lead to improvements in the clinical management of SLE.

Methods:

Aim 1: Ensure the Type 1 and 2 SLE model matches the patient experience with lupus.

We will conduct a qualitative, descriptive study. For objective #1, we will conduct in-depth interviews. For objective #2, we will conduct cognitive interviews. In-depth interviews will be completed prior to cognitive interviews. Information learned in the in-depth interviews to develop patient-reported measures will be reviewed in the cognitive interviews.

In-depth interviews: During the in-depth interviews, participants will be asked to share their perspective on the experience with Type 1 and 2 SLE symptoms, treatments, and how their experience with lupus fits with the Type 1 and 2 SLE model. (See attachment for the question guide).

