- **Physician-reported measures:** Systemic Lupus Erythematosus Disease Activity Index (SLEDAI), Physician's Global Assessment, LFA-REAL
- **Routine Lupus Labs:** CBC with differential, creatinine, C3 and C4, anti-dsDNA antibody, C-reactive protein, sedimentation rate, complete urinalysis, and urine protein:creatinine

Data Analysis: Robust cluster analysis. [name] will expand on our preliminary cluster analysis using latent profile analysis to include detailed patient-, physician- and laboratory measures. **Power Calculation:** In order to identify 4 clusters using 8 predictive variables, a minimum sample size of 320 patients is needed. If the cluster analysis identifies 7 distinct clusters, there will be sufficient power to include 5 predictive variables in the model with 350 patients. Differences in phenotypes across clusters, including patients' demographic, SLE history, patient- and physician-reported measures, and laboratory tests will be estimated by ANOVA and Chi-squared test.

Using our new knowledge about the quantitative differences in SLAQ responses by cluster, the qualitative information about symptoms from patient interviews, and clinical expertise, we will revise the SLAQ and create a new scoring system with individual Type 1 and 2 SLE scores. This new scoring system will be tested using 800 patient visits to determine if the new Type 1 and 2 SLE scores correspond to cluster assignment. Using logistic regression models, [name] will compare three commonly used physician-reported SLE measures, the SELENA-SLEDAI, physician's global assessment, and LFA-REAL™ to determine if model fit improves with physician-reported measures. Goodness of fit will be assessed by the Hosmer-Lemeshow chi-square test, and model discrimination will be assessed using C statistics to estimate the area under the receiver operating characteristic curve. To account for patients potentially contributing more than one visit to this analysis, generalized estimating equations (GEE) will be used.

Inclusion: Patients who are enrolled in the Duke Lupus Registry and gave informed consent through the Duke Lupus Registry (DLR) (IRB Pro00008875) and Sub-studies of the DLR (IRB Pro00094645).

Compensation: Data collected from patients enrolled in the Duke Lupus Registry will be retrospectively analyzed. No compensation will be provided as part of this analysis.

Aim 3. Conduct a pilot implementation study of the Type 1 and 2 SLE model into clinical care.

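### Aim 2 tests the new Type 1 and 2 scores against cluster assignment but not against the current SLAQ total or the FSS, so a good C statistic shows correspondence, not added value or retained performance with fewer items

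*Combined protocol and SAP*

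**What the plan says.** The Background gives the reason for re-scoring the SLAQ: "the current scoring system combines Type 1 and 2 SLE activity, resulting in an assessment that is not clinically actionable". Of the FSS it says "we have found this scale clinically useful to efficiently measure the current extent of Type 2 SLE symptoms", and Aim 1 (Participant selection and recruitment) uses an FSS of 12 or more to define high Type 2 symptoms. The plan is to "build a brief preliminary PRO measure that combines features of the FSS and the SLAQ".

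Aim 2, Data Analysis, forms clusters by latent profile analysis of patient, physician and laboratory measures. It then revises the SLAQ and builds separate Type 1 and Type 2 scores, drawing partly on how SLAQ responses differ by cluster. The test is: "This new scoring system will be tested using 800 patient visits to determine if the new Type 1 and 2 SLE scores correspond". The reference is cluster assignment. Logistic models then bring in the SELENA-SLEDAI, the physician's global assessment and LFA-REAL "to determine if model fit improves with physician-reported measures". Fit is judged by the Hosmer-Lemeshow test, and "model discrimination will be assessed using C statistics to estimate the area under the receiver operating characteristic curve". For repeat visits, "To account for patients potentially contributing more than one visit to this analysis, generalized estimating equations (GEE) will be used".

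Aim 2, Data Collection, lists a modified SLAQ and the FSS among the measures recorded at every registry visit.

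**The concern.** The argument for a new scoring is comparative: the present SLAQ score mixes two things that should be kept apart. The planned test is not comparative. It asks whether the new scores correspond to clusters, and whether physician measures improve the fit. Neither question involves the instruments the new measure is built from.

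The gap matters most for the Type 2 score. The plan already treats the FSS as an efficient Type 2 measure, so a respectable C for a Type 2 score that borrows FSS features is to be expected, whether or not the re-scoring contributed anything. Aim 2 also promises a parsimonious measure. Parsimony is a claim about how much performance survives when items are dropped, and it needs the longer instruments as the reference. As planned, Aim 2 could report a good C and leave both questions open.

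**Working it through.** **1. The plan's own figures.** The only sample-size statements in Aim 2 concern finding clusters: 320 patients for 4 clusters and 8 variables, and 350 patients for 7 clusters and 5 variables. No formula is given, but both equal 10 × clusters × variables: 10 × 4 × 8 = 320 and 10 × 7 × 5 = 350. No sample size, target C or comparator is stated for the test of the scores.

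**2. Is there a comparison anywhere?**
- Score test and logistic models (Aim 2): new scores and three physician measures. No SLAQ total, no FSS.
- ANOVA and chi-squared tests across clusters (Aim 2): these describe how patient-reported measures differ by cluster. They do not compare those measures with the new scores.
- Aim 3, Table 1: use, treatment, visit length, satisfaction, perceived quality and understanding. No comparison of instruments.

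**3. What one C can and cannot tell.** Illustration; every input is assumed. There are 800 independent visits and 300 simulated data sets. Latent Type 2 severity t is standard normal. A visit belongs to the target cluster if t + 0.5e > 0.5, with e standard normal. Each score is √ρ·t + √(1−ρ)·noise. The new score has ρ = 0.8 throughout; the existing score's ρ varies.

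| ρ, existing score | C, new | C, existing | New minus existing |
|---|---|---|---|
| 0.9 | 0.887 | 0.914 | −0.026 |
| 0.8 | 0.888 | 0.888 | 0.000 |
| 0.6 | 0.889 | 0.831 | +0.057 |

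(Differences are taken before rounding.) The reported result for the new score is the same in all three rows; its value relative to the existing score is not.

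**4. How precise would a paired comparison be?** Hanley-McNeil variance of a C statistic A with n1 visits in the target cluster and n0 outside:

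SE² = [A(1−A) + (n1−1)(Q1−A²) + (n0−1)(Q2−A²)] / (n1·n0), with Q1 = A/(2−A) and Q2 = 2A²/(1+A).

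For two scores on the same visits, with correlation r between their C estimates, SE(difference) = SE·√(2(1−r)). Assumed ranges: A 0.75 to 0.85, target-cluster share 25% to 50%, r 0.5 to 0.8.

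- 800 independent visits, least favourable (A 0.75, 25%, r 0.5): SE = 0.0216, SE(difference) = 0.0216, 95% half-width 1.96 × 0.0216 = 0.042.
- 800 independent visits, most favourable (A 0.85, 50%, r 0.8): SE = 0.0137, SE(difference) = 0.0087, half-width 0.017.
- Effective n of 320 (if repeat visits add little): half-widths 0.067 and 0.027.

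Differences detectable with 80% power at two-sided 5% are 2.80 × SE(difference): 0.024 to 0.060 at 800, and 0.038 to 0.096 at 320. The number of visits per patient is not stated, so the true position between these is unknown.

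**5. Circularity.** Patient-reported measures feed the clusters, and the new scores are shaped by SLAQ differences between clusters. The first favours the SLAQ and FSS as benchmarks; the second favours the new scores. In an illustrative check with assumed inputs, new scores minus SLAQ total plus FSS was +0.001 in C against the true clusters, but −0.016 against clusters estimated with the SLAQ total and FSS as inputs. The size depends on the inputs. The lesson is that the choice of reference alone can move the answer by as much as the difference of interest.

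**The case against.** The best defence is that the SLAQ's stated defect is structural. One total cannot separate two kinds of activity and two scores can, so beating the total is close to a foregone conclusion. The FSS covers Type 2 only, so neither parent is a like-for-like rival to a two-score output. The measure is also called preliminary, and the cluster ANOVA will show indirectly how existing measures separate the clusters. Much of this stands. It lowers the stakes and argues against a pass mark. It does not answer how the Type 2 score compares with the FSS, how the two scores compare with the SLAQ total and FSS together, or what is lost by shortening.

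A reader might infer three stronger things that the documents do not support:
- *That the new Type 2 score is meant to outperform the FSS.* The Background criticises only the SLAQ scoring; the FSS is praised and its features are borrowed.
- *That a good result would show nothing.* It would show correspondence with the clusters, which is what the plan says it will test.
- *That superiority over existing instruments is the premise for Aim 3.* Aim 3 rests on turning the Type 1 and 2 model into an actionable tool, and the PRO survey is one of five listed components.

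The circularity objection also stands: a comparison against the planned clusters alone would be hard to read. That calls for a second reference, not for leaving the comparison out.

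**Conclusion.** The omission is real. Aim 2 can establish that the new scores correspond to clusters and whether physician measures improve fit. It cannot establish added value over the SLAQ total or FSS, or retained performance with fewer items. This is a point the sponsor should address; it does not invalidate the planned test.

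The logic needs no simulated figure. The range from −0.026 to +0.057 only illustrates how little an isolated C says, and it follows from the assumed reliabilities. Existing data would give a paired difference with a 95% half-width of roughly 0.02 to 0.04 if the 800 visits behave as independent, and up to about 0.07 if the effective size is nearer 320. That is enough to describe the comparison and exclude large differences, but not enough to settle small ones. A reader might be tempted to make use of the new scores in SLE@Duke depend on a fixed loss in C, such as 0.02. The documents give no basis for such a margin, and the detectable differences above all exceed it.

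**What to change.** Add to Aim 2, Data Analysis:

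- On the same visits, with the same cluster coding and the same GEE logistic models, report C and calibration for (a) the current SLAQ total, (b) the FSS, (c) both together and (d) the new scores. State which SLAQ total is meant, since the registry collects a modified form.
- Report paired differences in C between (d) and each of (a) to (c), with a bootstrap interval that resamples patients, not visits, and repeats any data-driven scoring step in each resample.
- State that patient-reported measures enter the clusters and that the scores draw on SLAQ differences by cluster. As a sensitivity analysis, repeat the comparison with clusters formed without the SLAQ and FSS.
- Report the number of items beside each C, so that parsimony can be judged.
- Present the comparison descriptively, without a margin or a go/no-go rule for SLE@Duke.

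The cost is a paragraph in the plan, a few extra models and one re-clustering on data already held. The downside is a possibly less favourable message about the new scores.

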In-depth interviews: Interviews will be audio-recorded and transcribed verbatim. Nvivo, a qualitative research software, will be used to facilitate analysis. First, we will each apply the same structural codes to group similar responses together. Thematic coding will follow, focusing on identifying the main themes and sub-themes for each conceptual group (Guest 2006). Intercoder reliability procedures will be conducted; discrepancies in coding will be discussed, resolved, and revised as necessary. Thematic code frequencies across transcripts will be examined to identify the most frequent and salient themes, and data

reduction techniques will be used to explore the nuances and to identify sub-themes. Descriptions of these themes and sub-themes, together with illustrative quotes, will be collected in data summary reports.

Cognitive interviews: After each interview, the interviewer will complete a debriefing form to identify 1) SLAQ modifications, and 2) Type 1 or 2 symptom assignment. The debriefing forms from each interview will be summarized after each set of 10 interviews to determine the main themes, problems with the patient-reported outcomes measures that arose during the interviews, and suggested modifications to the measures. Following the second round of interviews, it will be determined if an additional 6 interviews are needed to assess the revised measure.

Aim 2: Develop a preliminary parsimonious measure to rapidly assess Type 1 and 2 SLE activity.

We will analyze data collected through the Duke Lupus Registry (DLR) (IRB Pro00008875) and Sub-studies of the DLR (IRB Pro00094645). Working closely with the Duke Center for Health Measurement, [name] will use patient- and physician-reported data collected from 800 patient visits in DLR to develop an effective and efficient indicator of Type 1 and Type 2 SLE activity.

Data Collection: Age, gender, race/ethnicity, employment status, marital status, living arrangement, and medication adherence will be ascertained by self-report. In addition, the DLR collects information from medical records including: insurance, medication details, disease duration, and comorbidities. The DLR also collects the following information at each clinic visit:

- **Patient-Reported Measures:** Modified Systemic Lupus Activity Questionnaire (SLAQ), Fibromyalgia Severity Scale, Patient global assessment, current medications

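### If the Aim 2 score is tested on the visits that shaped it, its C statistic will on average be modestly too high, and no internal validation is planned

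*Combined protocol and SAP*

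**What the plan says.** Aim 2 proceeds in three steps, all under Data Analysis.

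1. **Clustering.** A preliminary cluster analysis is extended "using latent profile analysis to include detailed patient-, physician- and laboratory measures". The indicators are not named. The Power Calculation counts patients: "In order to identify 4 clusters using 8 predictive variables, a minimum sample size of 320 patients is needed". A second case has 7 clusters, 5 variables and 350 patients.
2. **Scoring.** The SLAQ is revised and given separate Type 1 and Type 2 scores. The first input is described as "Using our new knowledge about the quantitative differences in SLAQ responses by cluster"; the others are the patient interviews and clinical judgement.
3. **Testing.** The scoring system "will be tested using 800 patient visits to determine if the new Type 1 and 2 SLE scores correspond to cluster assignment". With logistic regression the investigators "will compare three commonly used physician-reported SLE measures", the purpose being "to determine if model fit improves with physician-reported measures". Fit is judged by Hosmer–Lemeshow and discrimination by the C statistic.

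The Aim 2 introduction describes the development data as "data collected from 800 patient visits in DLR to develop an effective and efficient indicator of Type 1 and Type 2 SLE activity". Data Collection lists three physician-reported measures: SLEDAI, physician's global assessment and LFA-REAL. The one safeguard named is for repeat visits: "To account for patients potentially contributing more than one visit to this analysis, generalized estimating equations (GEE) will be used". No section mentions a hold-out sample, cross-validation, a bootstrap or an outside cohort.

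**The concern.** Cluster assignment helps to choose and score the items, and is then the criterion against which the score is judged. If both steps use the same visits, chance differences between clusters are built into the score and then counted as agreement. GEE allows for correlation between visits of one patient. It does nothing about this.

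Two further points follow from how the clusters are formed. If SLAQ answers are among the indicators, some agreement is guaranteed, even in new patients. And because physician measures enter the clustering and only three are listed, at least one measure tested for improved fit also helped define the outcome that it is asked to predict.

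This is the only quantitative test of the score that the protocol describes before a PRO survey enters the Aim 3 tools. Aim 3 itself assesses implementation by RE-AIM and does not test the score against clusters.

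**Working it through.** **Inputs from the protocol.** 800 visits for development (Aim 2 introduction) and 800 for the test (Data Analysis); 24 SLAQ symptoms (Background & Significance; the registry uses a modified form); 4 clusters, 8 variables, 320 patients, and 7 clusters, 5 variables, 350 patients (Power Calculation); minimal, Type 1, Type 2 and mixed activity (Background & Significance).

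**The plan's own figure.** N = m × clusters × variables. With m = 10, 10 × 4 × 8 = 320 and 10 × 7 × 5 = 350, both exact. With m = 5 the results are 160 and 175, and with m = 20 they are 640 and 700. The rule is not named, so m = 10 is inferred. These figures concern finding clusters, not testing a score.

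**Size of the bias, simulation 1.** Assumptions not in the documents: 350 patients with 800 visits; within-patient correlation 0.5; Type 1 high in 25% and Type 2 high in 35% of visits; 8 indicators including the SLAQ total; number of clusters chosen by BIC unless stated; 24 items scored 0–3 (8 Type 1, 8 Type 2, 8 noise); 10 items kept by F ratio and split into two sub-scores; logistic C averaged over clusters. There were 100 replicates, or 40 for the skewed case. New patients are classified by the same fitted clusters.

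| Shift in SD, indicators/items | C, same visits | C, new patients | Mean difference (5th–95th percentile) |
|---|---|---|---|
| 2.5/1.0 | 0.908 | 0.897 | 0.012 (−0.004 to 0.031) |
| 2.0/0.8 | 0.861 | 0.844 | 0.017 (−0.006 to 0.038) |
| 1.5/0.6 | 0.793 | 0.772 | 0.021 (−0.009 to 0.045) |
| 1.0/0.4 | 0.739 | 0.700 | 0.039 (−0.009 to 0.089) |
| 2.0/0.2 | 0.639 | 0.585 | 0.054 (0.020 to 0.094) |
| No classes, four clusters fixed, SLAQ total an indicator | 0.653 | 0.580 | 0.073 |
| No classes, four clusters fixed, SLAQ total not an indicator | 0.598 | 0.499 | 0.099 |
| No classes, 5 of 8 indicators right-skewed | 0.604 | 0.496 | 0.108 |

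With no classes and no skewness, BIC chose one class in 200 of 200 runs, so no test would arise. With skewed indicators it chose 6 or 7 clusters in every run.

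**Simulation 2, programmed separately.** This used 60 replicates per cell, four clusters, 350 patients with 800 visits, and item effects of 0 to 1.0 SD. The difference was above zero in all 24 cells: 0.003 to 0.049 for an unweighted sum of 8 selected items, and 0.010 to 0.124 for 24 data-derived weights. How far the weights come from the data therefore matters.

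**Agreement by construction.** In simulation 1, replacing the SLAQ total by a non-SLAQ Type 2 indicator lowered the new-patient C from 0.772 to 0.748 (1.5/0.6) and from 0.844 to 0.837 (2.0/0.8), which is 0.024 and 0.007. In simulation 2, with individual SLAQ items as indicators and no true SLAQ signal, the new-patient C was still 0.547 (unweighted) or 0.722 (weighted), against 0.499 and 0.494 for the true class.

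**Physician measures.** Gain in same-visit C from adding SLEDAI, simulation 1:
- 1.5/0.6: as an indicator, 0.846 − 0.793 = 0.053; clusters formed without it, 0.827 − 0.791 = 0.036; excess 0.017.
- 2.0/0.8: 0.903 − 0.861 = 0.042; 0.896 − 0.858 = 0.038; excess 0.004.

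**Does resampling repair it?** Patient-level five-fold cross-validation with every step repeated (30 replicates) gave out-of-fold C of 0.842 and 0.769, against new-patient values of 0.847 and 0.775 and same-visit values of 0.860 and 0.791. It removes the bias of 0.013 and 0.016 but undershoots by 0.005 and 0.006. If there are 350 patients, each training set holds 350 × 4/5 = 280, below the plan's 320; a half split would leave 175.

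**The case against.** A reader might infer that the protocol tests the score on its own development visits. It does not say so. The evidence is the equal count, the same registry, retrospective data and the absence of any second sample. That makes reuse the natural reading, but a separate set is not excluded.

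The clustering is sized in patients and the test in visits, so many test visits may never have entered the clustering. That is fair, but fitting the clusters on one record per patient left the simulated bias at 0.022 (1.5/0.6, four clusters fixed) and 0.017 (2.0/0.8).

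A reader might also infer that C overstates how well the score finds the true disease state. The direction holds only for new patients under the same clusters. Against the true class it can reverse: in simulation 2, with no SLAQ variable in the clustering and an item effect of 0.6 SD, the unweighted score had a same-visit C of 0.688 but 0.778 for the true class in new patients.

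The effect is small when clusters and items are informative, and in four of the five real-class settings the 5th–95th percentile range reaches below zero. Items were chosen wholly by F ratio, whereas the plan also uses interviews and expertise, which would reduce the bias. The C statistic is named for the logistic models; one for the score alone is not stated. All of this stands.

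Finally, it is tempting to say that an inflated C would trigger roll-out, or that agreement is presented as validation. The protocol sets no threshold for C, calls the measure preliminary, defers Aim 3 details to a later IRB submission, and asks only about correspondence with clusters.

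**Conclusion.** The concern holds in a conditional form. Building the score partly from cluster differences and testing it against the clusters without internal validation is stated; reuse of the visits is inferred. If the visits are reused, C for any model containing the score is too high on average. The likely size is 0.01–0.02 in favourable settings, 0.04–0.05 with weak separation or weak items, and 0.07–0.11 where no classes exist but several clusters are used, whether because their number is fixed in advance or because skewed indicators lead BIC to split. Heavier data-derived weighting can exceed these figures. They all rest on the simulation assumptions above. The uncorrected C is thus least reliable where the score is poor.

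The physician-measure point follows from the listed measures, taking those as the pool for the clustering. The simulated excess of 0.004–0.017 qualifies that comparison and does not void it. The plan should be amended, but the consequence is moderate.

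**What to change.** State whether the test visits come from patients other than those used for clustering and scoring. Then:

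1. **If they do not, bootstrap by patient**, keeping all visits of a patient together. In each resample repeat the clustering, including the choice of the number of clusters, and any algorithmic item selection or weighting. Hold interview- and expert-based choices fixed. State how clusters are matched across resamples. Report optimism-corrected C and calibration beside the apparent values. A bootstrap is preferred to splitting because each resample keeps the full number of patient draws. The bootstrap itself was not simulated here.
2. **Name the cluster indicators.** If SLAQ items are among them, interpret the result as agreement with the cluster construction, since resampling does not remove that part.
3. **Keep the planned clustering as the main analysis and add one sensitivity analysis** that compares all three physician measures against a single set of clusters formed without any of them. Removing each measure in turn would give three different outcomes and no common comparison.

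Any supporting check against SLEDAI should use clusters and scores formed without SLEDAI. A check against the fibromyalgia score should be dropped if its items enter the new score, which Background & Significance suggests they will.

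The cost is a few sentences, extra analysis and computing time, and no new data. The reported C will be slightly lower, with a wider interval.
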